### **Uniform research case definition for TBM **

It is proposed that patients suspected of having TBM be categorized into definite, probable, possible and no TBM. This is proposed to obtain standardization for research purposes, for adults and children, and was not primarily devised as a clinical tool. The clinical diagnosis of TBM (probable or possible) is based on clinical findings and special investigations (Table 1). The boundaries between groups are not fixed, and patients can interchange between groups, based on results of laboratory and radiological investigations. Definite TBM requires demonstration of acid-fast bacilli in the CSF, *Mycobacterium tuberculosis* culture from CSF, a positive nucleic acid amplification test (PCR) of CSF or histopathological evidence of *Mycobacterium tuberculosis* from a central nervous system site.

Patients must have a clinical diagnosis of meningitis including one or more of the following symptoms: headache, irritability, vomiting, fever and neck stiffness (Table 1). The diagnosis of probable or possible TBM is based on 1) clinical findings 2) CSF results 3) neuroimaging findings 4) evidence for TB outside the central nervous system and 5) additional laboratory criteria. A scoring system then determines whether a patient falls in the probable or possible TBM category (Table 1). Points are allocated for a positive finding in each of the categories, with a maximum score for each category. A total score of at least 10 is compatible with probable TBM, while a total score of at least 6 equates with a possible TBM diagnosis. A certain number of points have to come from the CSF or neuro-imaging criteria to ensure that the patient is indeed suffering from meningitis and not some other chronic type of tuberculosis. It is also suggested by the consensus

group that all patients should have additional CSF investigations to exclude alternative causes for the clinical presentation.

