## **Aims**

The main aims of the proposed project are as follows:

- 1) To validate a previously identified and patented three-marker CSF biosignature (IL-13, VEGF, cathelicidin LL37) for the diagnosis of TBM, in a new cohort of children with suspected TBM
- 2) To evaluate the usefulness of a recently identified and patented adult seven-marker serum protein biosignature (CRP, serum amyloid A, apolipoprotein A-1, transthyretin, complement factor H, interferon-gamma and IP-10) and other recently identified host markers, as a tool for the diagnosis of TBM
- 3) To investigate the usefulness of whole blood RNA transcripts as biosignatures for the diagnosis of TBM
- 4) To characterize the site of disease (CSF) versus peripheral blood immune profile of children with TBM, the response of immune cells to stimulation with *M.tb* antigens and explore differences between such responses in children with and those without TBM as part of student projects.
- 5) To develop a prototype point-of-care test based on host inflammatory protein biomarkers for

the rapid diagnosis of TBM (e.g. at the bedside) in children suspected of having TBM.

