#### **4. Diagnostic work-up**

All patients will undergo a comprehensive clinical evaluation (Addendum1). Routine special investigations will be performed. CT of the brain will be done in all probable TBM cases and in other cases of meningitis when indicated. Air- encephalography will be performed in all TBM cases with hydrocephalus. MR imaging will be done as clinically indicated. Lumbar puncture will be performed and the following CSF investigations performed: appearance and colour determination; differential cell count determination by standard methods; protein, glucose and chloride determination by standard methods; centrifugation with Gram stain and India ink examination of the deposit; culture of the centrifuged deposit on blood agar plates for pyogenic bacteria; Auramine “O” staining & fluorescence microscopy, culture using the BBL™MGIT(Mycobacterium Growth Indicator Tubes)™ of Becton and Dickinson and detection of *Mtb* DNA using the HAIN Genotype MTBDRplus kit. Samples will be tested using Xpert Ultra and newer technologies e.g. AlereQ TB and the Savannah MTB assay. Microbiomic analysis will be performed on microbial DNA extracted from patient specimens and sequenced on the Illumina MiSeq platform. All data will be recorded on a pre-designed clinical data capture sheet (see addendum) and entered into a computerized database. Finally, data analysis will be carried out using appropriate software and statistical packages.

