#### **The diagnosis of TBM will be made based on the following criteria:**

A diagnosis of **probable** TBM will be made if two or more of the following criteria are present in the setting of a characteristic history and CSF changes associated with TBM: A positive history of contact with an adult TB case, a positive tuberculin skin test, a chest x-ray suggestive of pulmonary tuberculosis (hilar lymphadenopathy, miliary tuberculosis or cavitation, CT or MRI demonstrating the characteristic features of TBM (ventricular dilatation, meningo-vascular enhancement and/or granuloma/s), poor weight gain or weight crossing percentiles documented on the Road to Health Card or positive identification of acid fast bacilli from gastric washings (microscopy or culture).

A diagnosis of **definite** TBM will be made if acid-fast bacilli is present in the CSF, *Mtb* is cultured

from CSF, a nucleic acid amplification test of CSF is positive or there is histopathological evidence of *Mtb* from another central nervous system site. The degree of TBM will be classified according to the proposed modified British Medical Research Council (BMRC) classification of 1948. -Stage I: Glasgow Coma Scale (GCS) of 15 and no focal neurology, Stage IIa: GCS of 15 plus focal neurology, Stage IIb: GCS of 11-14 with focal neurology, Stage III: GCS <11. All investigations required for establishing a diagnosis (TBM or no TBM) are usually done routinely and shall therefore not specifically be as part of the current study.

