## **Collection and processing of samples for the proposed study**

All samples required for the current study shall be collected during specimen collection for routine diagnosis. That is, specimens shall not specifically be collected from any study participant solely for the purposes of this study. During the collection of samples (CSF and whole blood) for routine clinical investigations, the alcohol swab used to sterilize the puncture site will be collected and

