### **Statistical methods and analysis plan**

Differences in the concentrations of individual host biomarkers between participants with TBM disease and those without TBM shall be evaluated by the Mann–Whitney U-test for non-parametric data analysis or the students t test, if data is normally distributed. P-values shall be deemed significant if less than 5%. The diagnostic accuracy of individual host biomarkers shall be investigated by receiver operator characteristics (ROC) curve analysis. The predictive abilities of combinations of analytes (biosignatures) shall be investigated by General discriminant analysis (GDA), random forests, and other biomarker analysis techniques, following the training/test set approach as done in previous studies . For Flow cytometry data, cell gating and data analysis will first be carried out on FlowJo software (Oregon, USA), followed by parametric (t-test) or non-parametric (Mann-Whitney U-) tests to assess the differences in quantities of immune cell

subpopulations, intra and extracellular cytokines and other biomarkers among children with TBM and those with other meningitis. Kruskall-Wallies test or one-way ANOVA with post-hoc analysis will be performed for comparison of more than 2 groups as advised by bioinformaticians from the Division of Molecular Biology and Human Genetics.

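### Aim 1: probable TBM is partly defined by CSF findings, and the plan has no definite-only analysis and no comparison of the CSF signature with routine CSF results

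*Combined protocol and SAP*

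**What the plan says.** The diagnostic criteria in section 4 (Diagnostic work-up) set two routes to a case label.

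- **Probable TBM** needs at least two supporting features (such as TB contact, skin test or imaging), and these count only "in the setting of a characteristic history and CSF changes associated with TBM". The criteria do not say which CSF measures or cut-offs are meant.
- **Definite TBM** is microbiological or histological. A diagnosis of definite "TBM will be made if acid-fast bacilli is present in the CSF", or on a positive CSF culture or nucleic acid test, or on histopathology "from another central nervous system site". No cell count or chemistry threshold applies.

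Section 3 pools the two as the target group (at least 72 children, within a total of up to 460). The other children have bacterial meningitis, viral meningitis or normal CSF.

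Aim 1 is "To validate a previously identified and patented three-marker CSF biosignature (IL-13, VEGF, cathelicidin LL37) for the diagnosis of TBM". The research CSF comes from the routine collection: "All samples required for the current study shall be collected during specimen collection for routine diagnosis". The routine work-up in section 4 includes "differential cell count determination by standard methods; protein, glucose and chloride determination by standard methods", and all data go onto the data capture sheet.

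For single markers the Statistical methods and analysis plan states: "The diagnostic accuracy of individual host biomarkers shall be investigated by receiver operator characteristics (ROC) curve analysis". Signatures are assessed by discriminant analysis and random forests with training and test sets. The section mentions no analysis restricted to definite TBM, no routine-CSF comparator and no added-value model.

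**The concern.** The reference label and the index test draw on the same fluid. A child without definite TBM becomes a case only if the routine CSF already looks like TBM. A CSF protein that rises and falls with the routine findings will then agree with the label partly because of how the label was made. A training/test split does not help, because both parts carry the same label.

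Two questions would go unanswered. One is how much of the observed accuracy comes from the label. The other is whether the signature tells the clinician more than the cell count, protein and glucose from the same puncture. The stated overall aim is diagnostic utility, so the second question matters even if the first effect is small.

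**Working it through.** **The plan's own figure.** The 72 and 460 in section 3 come from a two-proportion calculation, but the two proportions and the power are not given. They cannot be reproduced from the document, and this point does not depend on them.

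**Where CSF enters the label.**

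| Group | Role of routine CSF cell count and chemistry |
|---|---|
| Probable TBM | Necessary (CSF changes), with history and at least two non-CSF features |
| Definite TBM | None required |
| Bacterial or viral meningitis controls | Not stated as a requirement |
| Normal-CSF controls | The group is named by its CSF result |

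The cited uniform research definition also relies on CSF: "A certain number of points have to come from the CSF or neuro-imaging criteria". There, however, imaging points can stand in for CSF points.

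**Illustration of size.** The documents give no inputs for this, so every value except the prevalence is assumed:

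- True TBM prevalence is 72/460 = 15.7%.
- The routine CSF score has SD 1 and is shifted by δ in true TBM.
- The marker only echoes that score (correlation 0.9) and has no other information. Its true AUC is Φ(0.9δ/√2).
- 20, 40 or 60% of true cases are confirmed (definite), regardless of the CSF score.
- The supporting features are met by 80% of true cases and 15% of others.
- A child who is not definite is labelled probable if those features are met and the CSF score exceeds 0.5.

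| δ | True AUC (simulated) | AUC against the label at 20 / 40 / 60% confirmed | AUC, definite cases v children with no TBM label |
|---|---|---|---|
| 0 | 0.50 | 0.734 / 0.675 / 0.632 | 0.526 / 0.523 / 0.518 |
| 0.5 | 0.62 | 0.785 / 0.746 / 0.717 | 0.639 / 0.639 / 0.640 |
| 1.0 | 0.74 | 0.827 / 0.806 / 0.792 | 0.746 / 0.749 / 0.751 |
| 1.5 | 0.83 | 0.860 / 0.853 / 0.846 | 0.832 / 0.835 / 0.837 |

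The largest inflation is 0.734 − 0.499 = 0.235 and the smallest is 0.846 − 0.831 = 0.015. It shrinks as more cases are confirmed and as routine CSF becomes truly informative. Restricting cases to definite TBM brings the AUC close to the truth. The small remainder arises because high-scoring children labelled probable have been removed from the comparison group. In every row the routine score itself does better against the label than the marker (for example 0.764 against 0.734), which only a head-to-head comparison would show.

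**Precision of a definite-only analysis.** The number of definite cases is not stated. If 20–60% of 72 are definite (assumed), that is 0.2 × 72 ≈ 14 to 0.6 × 72 ≈ 43 children. Wilson 95% interval around the pilot sensitivity of 52%: centre (p + z²/2n)/(1 + z²/n), half-width z√[p(1−p)/n + z²/4n²]/(1 + z²/n).

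- n = 14: 28–75%
- n = 43: 38–66%
- n = 72 (all TBM): 41–63%

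**Power for added value, even with all 72 cases.** For a paired comparison of sensitivity (two-sided 5%, 80% power), n = [1.96√ψ + 0.842√(ψ − d²)]²/d², where d is the gain and ψ the discordant share. For d = 0.10 and ψ = 0.20 / 0.30 / 0.40 (assumed), n = 155 / 234 / 312. With 72 cases the power is 47 / 34 / 27%.

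**The case against.** The strongest reply is that stand-alone accuracy is a legitimate target for a validation aim, and that added value is a further question. That stands. The plan is not wrong to report an AUC; it lacks the analyses needed to interpret it.

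Four stronger readings are tempting, and the documents do not support them.

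- **That the whole label requires abnormal CSF.** It does so only for probable TBM. Even there CSF is necessary but not sufficient, and reading the unspecified CSF changes as cell count and chemistry is an inference.
- **That the index test is built into the reference standard.** IL-13, VEGF and LL-37 are not in the criteria. Any inflation runs through their correlation with routine findings, which is not given.
- **That a merely redundant signature would be declared validated and put into a device.** No success threshold is stated. The pilot signature reached 52% sensitivity at 95% specificity, whereas the echo marker in the illustration reached only about 10–35% at that specificity against the label. It would visibly fall short. The Literature review also describes the blood-based signatures, not the CSF one, as ready for point-of-care use.
- **That such a signature could change no diagnosis.** Aim 5 seeks a rapid bedside test, and speed could matter on its own.

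The hypothesis compares TBM with other forms of meningitis. Bacterial and viral meningitis also alter CSF, so a generic inflammation marker would separate these groups less well. The effect should be greatest against normal-CSF controls, whose share is not stated. This limits the size but does not remove the point.

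**Conclusion.** The point holds in a limited form. Because CSF changes are a precondition for probable TBM, and probable is pooled with definite TBM, the aim 1 accuracy estimate can be too high among probable cases to the degree that the markers follow routine CSF findings. The documents do not allow the size to be fixed. The range of about 0.015 to 0.235 AUC rests on assumed prevalence, confirmation rates, cut-off and correlation, and shows direction and plausible spread only. As written, the plan cannot detect the inflation or show added value. The point covers aim 1 and other CSF markers. The blood signatures are not measured in the fluid that helps define the label, so the argument does not extend to them. This should be changed, but it does not invalidate the study.

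**What to change.** Add to the Statistical methods and analysis plan, for aim 1:

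1. Report the pre-specified signature's AUC and its sensitivity at 95% specificity, with 95% confidence intervals, for definite TBM separately from all TBM. In the definite-only analysis, leave probable cases out rather than counting them as controls.
2. Report these results against bacterial and viral meningitis controls separately from normal-CSF controls, because the latter are named by their CSF result.
3. In the same children, report the accuracy of a small pre-specified routine-CSF model (for example cell count, % lymphocytes, protein, glucose) alone and with the signature added. Give the change in AUC with its 95% confidence interval.

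Make definite TBM against other meningitis the main added-value comparison. Keep the all-TBM version as secondary, with a stated caveat that routine CSF is favoured there because it helps define probable TBM. Present all of this as estimation, not as a powered test.

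The change needs SAP wording and some analysis time; the variables are already recorded. The real cost is precision. With 14–43 definite cases (assumed) the intervals are wide, so the routine model must stay small and the added-value result may be inconclusive. Confirmed cases may also differ from unconfirmed ones, which is why both sets of results are needed.

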### **Use of host biomarkers in the diagnosis of TBM**

Recent technological advances have made it possible to screen for many biomarkers in as little as 3 µl of sample using the Luminex multiplex cytokine beaded arrays. Using the Luminex platform, it is now possible to simultaneously detect the levels of 100 biomarkers in 3 to 50 µl (if using the Luminex/Bio-Plex 200 platform) and up to 500 markers if using the Luminex FlexMap 3D system. This platform has enabled the identification of novel host protein biomarkers for several diseases including TB. In previous studies, some of which were pioneered by our research group at

Stellenbosch University, novel biomarkers were detected in adult Quantiferon supernatants, which allowed for discrimination between TB disease and latent infection . When the biomarkers identified in adults were investigated in children, a biosignature comprising of four markers diagnosed paediatric TB disease with an accuracy of 84% .

In a recently concluded large multi-centred pan-African study (the African European Tuberculosis Consortium –[www.ae-tbc.eu](http://www.ae-tbc.eu)), we observed that some of the markers that frequently showed potential in our previous TB-antigen stimulation studies performed best either individually or in multi-marker models when measured in unstimulated supernatants. Further work on ex vivo serum biomarkers in 716 individuals that presented signs and symptoms suggestive of TB, prior to clinical diagnosis in five African countries (Namibia, Uganda, Malawi, The Gambia and South Africa), resulted in the identification of a seven-marker serum biosignature, which diagnosed TB disease in adults with high accuracy .

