### **3. Inclusion and exclusion criteria:**

All children between the ages of 3 months and 13 years with suspected meningitis, and who require CSF examination for routine diagnostic purposes at Tygerberg Children's Hospital, where written consent is obtained will be included. If possible, assent will be obtained in those children older than 7 years who have a normal level of consciousness, i.e. a Glasgow Coma Score (GCS) of 15/15. Children 13 years and older will be excluded from the study. Failure to obtain written consent will also exclude children from the study.

The anticipated study period is November 2016 to December 2025. The estimated sample size, using a two-sample comparison of proportions (STATA®-Statistics/Data Analysis), required for each of the diagnostic aims of the study includes, at least, 72 children with definite or probable TBM and a total sample size of up to 460 patients (This includes children with TBM, bacterial

meningitis, viral meningitis and normal CSF). An average of 40 new TBM cases is admitted to our wards annually.

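### Every probable TBM label needs a sign from outside the CNS, so the blood signatures of aims 2 and 3 may partly measure TB anywhere, and the planned analysis would not show it

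*Combined protocol and SAP*

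**What the plan says.** Under the diagnostic criteria in section 4, probable TBM applies when "two or more of the following criteria are present in the setting of a characteristic history and CSF changes associated with TBM". The six criteria are:

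- three in one run: "A positive history of contact with an adult TB case, a positive tuberculin skin test, a chest x-ray suggestive of pulmonary tuberculosis";
- imaging: "CT or MRI demonstrating the characteristic features of TBM";
- two more: "poor weight gain or weight crossing percentiles documented on the Road to Health Card or positive identification of acid fast bacilli from gastric washings".

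Definite TBM rests on acid-fast bacilli, culture or nucleic acid amplification in CSF, or on CNS histology. It requires none of the six.

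Section 3 pools the two grades, asking for at least "72 children with definite or probable TBM" within a total of up to 460. Aim 2 is "To evaluate the usefulness of a recently identified and patented adult seven-marker serum protein biosignature"; the literature review describes that signature as one "which diagnosed TB disease in adults with high accuracy". It describes the RNA signatures behind aim 3 as developed for active TB, or the risk of it, and concedes that their value in childhood TBM is unknown.

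The statistical methods section compares biomarkers "between participants with TBM disease and those without TBM", followed by ROC curves and multi-marker models with a training/test approach. It has no split by diagnostic certainty and none by TB outside the CNS.

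The literature review also outlines a score-based consensus definition of probable TBM, whose table is not in the text available for review. Section 4 states the rule that the study will apply, so the check below uses that rule.

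**The concern.** The reference label for probable cases draws on evidence of TB exposure, infection or disease outside the CNS. The blood signatures were built to respond to TB disease. Label and index test can therefore agree through a shared cause that is not meningitis.

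A training/test split does not protect against this. Both halves carry the same labels and case mix, so a signal for TB anywhere that is learned in one half reappears in the other as apparent accuracy for TBM. The same holds for the new markers and new RNA signatures that the plan allows under these aims.

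At stake is what may be claimed. The literature review expects validated blood signatures to be ready for point-of-care use. The child in whom a TB-anywhere signature would mislead is the one with TB elsewhere and bacterial or viral meningitis, and the plan neither counts nor analyses such children.

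**Working it through.** **The plan's own figure.** The 72 cannot be reproduced: the two proportions, the power and the allocation ratio are not given. Unrelated pairs land near it at two-sided 5% (35% against 15% at 80% power, 1:1, gives 73; 45% against 20% at 90% power, 1:1, gives 72). It can be neither confirmed nor called wrong, and this point does not depend on it.

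**Step 1: counting the rule in section 4.**

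- Minimal pairs: 6 × 5 / 2 = 15. All qualifying sets of two or more: 2^6 − 1 − 6 = 57.
- Only one criterion concerns the CNS, so no qualifying set is CNS-only.
- Pairs that include imaging: 5. Pairs that need no imaging finding: 10 of 15.
- The five non-CNS criteria: two show TB disease (chest x-ray, gastric washings), one infection (skin test), one exposure (contact), and one is non-specific (poor weight gain). Four of five are TB-related; two of five show disease.
- Pairs with neither chest x-ray nor gastric washings: 4 × 3 / 2 = 6 of 15. Sets: 2^4 − 1 − 4 = 11 of 57.
- Pairs with no TB-specific sign outside the CNS: one (imaging plus poor weight gain).

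These are counts of combinations, not of children. The documents do not say how often each combination occurs.

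**Step 2: how a test blind to the CNS would perform.** All inputs are assumptions. The test is positive in 80% of children with TB elsewhere and 10% of those without. Let a be the share of TBM cases with TB elsewhere and b the share of controls.

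- Apparent sensitivity = 0.80a + 0.10(1 − a). At a = 0.50: 0.40 + 0.05 = 45%. At a = 0.70: 0.56 + 0.03 = 59%.
- Apparent specificity = 1 − [0.80b + 0.10(1 − b)]. At b = 0.05: 1 − (0.04 + 0.095) = 86.5%. At b = 0.20: 1 − (0.16 + 0.08) = 76%.
- Specificity among controls with TB elsewhere: 1 − 0.80 = 20%, whatever b is.
- Sensitivity + specificity − 1 = 0.70(a − b). At a = 0.50: 0.315 for b = 0.05 and 0.21 for b = 0.20. At a = 0.70: 0.455 and 0.35.

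Apparent discrimination thus depends only on how much more common TB elsewhere is in cases than in controls.

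**Step 3: precision of the split results.** Half-width = 1.96 × √[p(1 − p)/n].

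- Assume 36 of the 72 cases are definite, and borrow 52%, the sensitivity reported for the CSF signature: 1.96 × √(0.52 × 0.48 / 36) = 0.163, about ±16 points.
- With 460 − 72 = 388 controls, 5% is about 19 children and 20% about 78. At 20% specificity the half-widths are 1.96 × √(0.16/19) = 0.18 and 1.96 × √(0.16/78) = 0.09 (a rough approximation at n = 19).

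**The case against.** - **TB elsewhere is not enough for the label.** A characteristic history and TBM-type CSF changes are mandatory. This stands and limits the concern. It does not remove it, because a blood marker need not reflect the CSF.
- **The link between label and signature is partial.** Only two of the five non-CNS criteria show TB disease, which is what the signatures were built to detect. This stands.
- **The label effect is confined to probable cases.** Definite TBM needs no sign outside the CNS, and the probable share is not given. A reader might infer that all cases are selected to have TB elsewhere; the documents do not support that.
- **Controls may also have TB elsewhere.** A reader might infer that controls mostly lack it. Section 3 enrols all children with suspected meningitis and excludes nobody for TB elsewhere, in a country with a stated incidence of 834 per 100,000. Such controls could expose a TB-anywhere signature, but only if they are identified and analysed.
- **The illustration models co-occurring TB, not bias from the label.** The figures in step 2 would be the same if every case were definite. They show what the planned comparison cannot distinguish, not how far the case definition inflates accuracy. Nor is 45% with 86.5% impressive: with 72 cases and 388 controls, the positive predictive value is 32.4 / (32.4 + 52.4) = 38%.
- **The stated contrast is TBM against other meningitis.** Within that contrast a blood marker of TB can be useful without being specific to the meninges. This stands, so the pooled comparison is not invalid. What it cannot support is a claim that the signature is specific to TBM.

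**Conclusion.** The concern holds in a limited form. It is exact that every probable label needs at least one criterion from outside the CNS. It is also clear that the aim 2 signature and the published aim 3 signatures come from TB disease in general, that definite and probable cases are pooled, and that the analysis has no comparison able to separate TBM from TB elsewhere. Aims 2 and 3 may therefore partly measure TB anywhere; the documents do not show that they do. Aim 1, the CSF signature, is outside this point.

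The size cannot be fixed from the documents. It depends on the probable share and on how common TB elsewhere is in cases and controls, none of which is given. On the assumptions in step 2, the gap that matters is between an overall specificity of 76% to 86.5% and 20% in controls with TB elsewhere. A reader might conclude that the pooled result should give way to definite TBM alone. That goes too far: the protocol reports low smear and culture sensitivity and about 50-60% for GeneXpert, so unconfirmed cases are where a new test is most needed.

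**What to change.** In the statistical methods section, for aims 2 and 3, keep the pooled definite-or-probable analysis and pre-specify these secondary results, each with confidence intervals:

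- (a) sensitivity separately for definite and for probable TBM;
- (b) specificity in no-TBM children with and without chest x-ray or gastric-washing evidence of TB, with skin-test status shown separately, and with untested children as their own group and not counted as negative;
- (c) sensitivity in definite TBM without chest x-ray or gastric-washing evidence of TB.

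State that a blood signature will not be described as specific to TBM, as opposed to TB disease in a child with meningitis, unless (b) and (c) support it. The level that counts as support should be written down before the data are seen.

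The cost is mainly analysis wording, with no added samples. The downsides are wide intervals, a possibly small group of controls with TB elsewhere, and a different disease spectrum in definite cases. Work-up may also be incomplete in some controls. Section 4 says only that the diagnostic investigations are usually routine, its work-up list does not name chest x-ray, skin test or gastric washings for every child, and the data capture sheet is not in the text available for review. Completeness of these three tests should be checked and reported.
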